As additional safeguards, **if a child reveals substantial mental health problems, such as suicidal ideation/attempts, homicidal ideation, or clinical deterioration, or if such problems are identified during the course of the study**, the child will be evaluated as soon as possible, by the PI, the primary mentor, and (if indicated) the on-call RIH psychiatric crisis team, to make a clinical determination about whether the child requires hospitalization or other clinical services. The primary mentor is a licensed child clinical psychologist and has training and experience in intervening in similar crisis situations. Project staff will carry cell phones with them during all participant contact and will be instructed to contact the PI (who is on call and always carries a phone) immediately to inform her of any clinical emergency. Additionally, [name] and [name] will carefully monitor the symptom progression of all participants. **If a patient is deemed to need psychiatric hospitalization based on the screening, they will be withdrawn from the study.**

If any mental health problems are reported or identified at the time of the follow-up and the family is not in treatment, appropriate referral for psychological intervention will be arranged.

Whenever possible, study staff will handle these situations therapeutically. For example, if time limits and safety concerns allow, parents will be informed in advance and provided the opportunity to participate in the mandated report process. Research staff will contact the PI who will be responsible for any on-site clinical decision-making.

Over the past 10 years, in several ED studies conducted by myself and my mentors, staff have encountered only 2 cases of harm to others that involved crisis management procedures leading to breaching confidentiality and involving authorities, less than 10 cases of child abuse requiring mandatory reporting to the police, and regular suicide risk assessments (~10 participants per study, per month).

14c. Potential benefits of the proposed research to the subjects and others:

Participation in this project could potentially benefit participants in a few important ways. The instruments used to obtain information in this study are commonly used in clinical and research practice but may invoke some emotional discomfort. Efforts will be made to minimize this discomfort by presenting questions in a supportive manner, assuring participants that they may refuse to answer questions that make them uncomfortable, and may terminate participation in the study at any time. It is also possible that the questions or assessments themselves may be beneficial to all participants by asking them to review their affect and peer violence. The screening and baseline assessments may therefore act as a very minimal intervention (as could any study with interviews regarding risky behaviors). Indeed, study participants in [name] and [name] previous, similar studies have commented that they have found the questions to be helpful.

Additionally, we hope that our intervention will be successful in preventing/reducing depressive symptoms, and possibly peer violence, in our subject population. The intervention offers the possibility of a relatively low-resource, highly-disseminable preventive intervention for a needy population. We therefore think that the clear examination of these questions outweighs the previously mentioned risks.

Because all youth participating in the study self-report depressive symptoms and peer violence, we felt it was necessary to enhance usual care (typically no violence-prevention or mental health information is routinely provided during the ED visit) for all youth. Thus, all youth participating in screening will review a health information brochure, with referral information for mental health problems including suicide hotlines, substance

use, and violence prevention and treatment services, anger management, etc. This pamphlet will be similar in style and content to that used in my mentors' prior work. In addition, as described above, participants that meet criteria for severe depressive symptoms or suicidality on the screening survey will be offered a clinical assessment and individualized referral in the ED, which exceeds the current standard of care.

In sum, potential benefits for the research far outweigh the risks for the participants. The proposed research also has significant benefits for society in general, as described in **Importance of the Knowledge to be Gained** (14d, below).

14d. Importance of the Knowledge to be Gained

Given the high rates of both depression and peer violence among youth; the interdependence of these problems; the individual and societal cost of violence and its mental health consequences; the fact that most of these teens use the ED as their primary source of care; and these teens' lack of access to traditional mental health services; the development of effective targeted interventions are clearly needed. Given the paucity of accessible existing interventions, the knowledge to be gained from this research is significant. The risks to participants are reasonable in relation to the importance of this knowledge to be gained.

14e. Vertebrate animals:

n/a

14f. Data and Safety Monitoring Plan

To address the NIH policy for Data and Safety Monitoring, the PI ([name]) and her mentorship team have developed a system for oversight of the proposed study and its participants. The Data and Safety Monitoring Plan for this application will begin by implementing standard procedures for day-to-day monitoring of the study. The Principal Investigator, [name], will be responsible for monitoring the data quality and safety. As already noted above, all research projects involving human participants at Rhode Island Hospital, including this proposed study, require approvals from the Rhode Island Hospital (RIH)/Lifespan Institutional Review Board (IRB). In addition, because of the sensitive nature of the data being collected, a Certificate of Confidentiality will be obtained for this study from the National Institute of Health (NIH).

[name] will ensure that all relevant IRB policies, procedures and stipulations are being followed. [name] also will be responsible for ensuring that other investigators and project staff adhere to the RIH IRB policies including the following: (1) All participants in the full Aim 2 and Aim 3 studies will understand, agree to, and sign a written assent form (and consent from parent/guardian) before participating; (2) Strict adherence to a participant's right to withdraw or refuse to answer questions will be maintained; (3) All interviews and assessments will be completely confidential and no names will be associated with the data; (4) Consent forms and identifying information will be kept separate from the actual participant data; (5) All identifying information (consents, tracking data) will be kept locked at all times and computer files will be saved with passwords; and (6) Participants will be informed in writing in the consent form on how to contact the PI, the study coordinator, and IRB office with any questions and/or concerns.

Weekly meetings with [name] will be conducted to evaluate the progress of the trial and to review data quality, recruitment, study retention, and examine other factors that may affect outcome. Participant experiences and the rates of adverse events will also be reviewed to determine any changes in participant risk. [name] will report any adverse events that are observed to the IRB within one week of occurrence, and to NIMH in our annual report. Serious adverse events (SAEs) will be reported to the IRB within 2 work days of our receipt of information regarding the event; if deemed to require a change in protocol, NIMH will also be notified. Reports of changes or amendments to the protocol in general must be requested first in writing to the IRB, which then will grant or deny permission to make the requested change or amendment in protocol.

Finally, if significant homicidal, suicidal, or mental health risks occur during the study period, the participant's parent(s) will be notified, as described in **14b.2. Protection against risks** (above), and evaluation by the Rhode Island Hospital crisis team will be immediately initiated to determine whether hospitalization is needed.

In the event that a research participant either withdraws from the study or the investigator decides to discontinue a research participant due to SAE, the research participant will be monitored by the investigator via ongoing status assessment until either a resolution is reached (i.e. the problem requiring hospitalization has resolved or stabilized with no further changes expected), the SAE is determined to be clearly unrelated to the study intervention, or the SAE results in death.

Independent evaluators from the Department of Emergency Medicine and the Department of Psychiatry will be incorporated into the existing Data Safety & Monitoring Board (DSMB) in the Department of Emergency

Medicine, to assist with study-specific ongoing monitoring of data. These additional members will include [name] (pediatric emergency physician and chair of the Lifespan IRB, Dept of EM, Brown University); and [name] (emergency physician and researcher in the overlap between alcohol abuse and injury, Dept of EM, Brown University). This enhanced Dept of EM DSMB, as an adjunct to the IRB, will have control and independence in offering recommendation arising from participant concerns or adverse events related to our study, or stopping the study for the benefit of our participants. This DSMB will convene once yearly, and as needed, and produce a written report. This report will be sent to the Lifespan IRB as well as to the project officer at NIMH. The DSMB will review all serious or unexpected adverse events to determine any changes in participant risk and provide recommendations.

Participants will only be identified by number during review of study progress by the DSMB. In the event that confidentiality must be breached, only the PI and Primary Mentors would be informed of identifying information in order to report to the appropriate authorities or health care providers. In the event that a conflict of interest within the DSMB is identified, the DSMB will disclose the matter to the Lifespan IRB. The DSMB will provide recommendations to the PI on how to resolve the conflict of interest, and the PI will report and document the action to the Lifespan IRB.

14g. Educational Training

Since October 1, 2001, Lifespan has required that researchers and IRB members read Protecting Study Volunteers in Research (Dunn & Chadwick) and complete the related exam. This process has served as initial certification between 10/2001 and 5/2005. In June, 2005, the Office of Research Administration contracted with CITI, a Collaborative Institutional (modular) Training Initiative program, for our Human Subjects protection and HIPAA training for all research personnel. Currently this program offers our researchers a basic human subject's protection course as well as a refresher course which we require every three years. Documentation of successful completion is automatically generated and should be printed directly by the researcher. For further information regarding Lifespan's Human Subject's Protection course go to: <http://www.lifespan.org/research/IRB/MandatoryEdguidance.asp>

Additional and continuing education opportunities for clinical researchers include the Office of Research Administration newsletter that is circulated to > 900 recipients every 6 weeks. Relevant information concerning research review is available on the ORA web page at www2.lifespan.org/research/. In addition to standard institutional research information, the web page contains links to other sites such as CenterWatch, NIH, PRIM&R/ARENA.

Finally, the PI will participate in the training in the Responsible Conduct of Research detailed in Section 5, above.

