Screening and Consent. A research assistant (RA) will be present in Hasbro Children's ED on randomly selected shifts (selection weighted according to patient volume). All patients between ages 13 and 17 will be pre-screened by the RA. If the patient is triaged as stable, and is not presenting for with a chief complaint of suicidality, psychosis, sexual assault, or child abuse, the RA will approach the patient and his/her family once the patient is put in a private treatment room. After reading a script to the parent and child, verbal consent/assent will be obtained from the parent/legal guardian and the child. Then, youth will complete a computerized screening survey. The adolescent and his/her parent will be informed that the adolescent's answers to study questions may be used to determine their eligibility for a research program. After completion of assent/consent, the teen will then be administered the screening questionnaire, including PHQ-9, and CTS-2. Additionally, to reflect my experience with 2 different screening processes during my pilot grant, we will administer additional questions drawn from Add Health, YRBS, and other relevant materials about other behaviors (which I and my mentors have found increases participant honesty on all questions; in studies where we only administer the screening questions of interest, rates of self-report have decreased significantly). All participants will be able to choose a small gift (worth \$1-2) as compensation for their time.

If an adolescent screens positive for mild-to-moderate depressive symptoms (PHQ-9 between 5 and 20) and past-year peer violence, s/he will be informed that they are eligible for the research program. Adolescents and their parents will be informed that their responses to screening questionnaire indicate that they are eligible for a program to help build mental health and prevent fights. Screened participants who agree to be part of the study will complete an additional *written* assent/consent form for Aims 2 and 3.

All individuals who agree to participate in the screening will be given referral information for a variety of community resources including community mental health services and violence prevention organizations.

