During recruitment, research staff will inform the subject of the general nature of the study, their privacy rights, expectations for their participation, the voluntary nature of their participation, and that their participation can be withdrawn at any time. Participants will be assured that refusal to participate will not affect their care in any way. At all times, research staff will make explicit the voluntary nature of the subjects' participation as well as potential situations for breaking confidentiality. Recruitment procedures will be HIPAA compliant and have been IRB approved in past studies.

Referrals. All participants in the screening will receive a handout of mental health and violence prevention resources. If an adolescent screens positive for severe depressive symptoms at any time during the study, regardless of eligibility for the study, the RA will discuss the score with the family, notify the attending pediatric emergency physician, and offer to contact the adolescent's pediatrician.

If an adolescent discloses suicidality or if the patient's family so desires, the RA will alert the patient's clinician (if appropriate) who will immediately initiate a psychiatric evaluation in the ED, or will contact the patient and his/her parent if disclosure occurs outside of the ED. (See "Mandatory Reporting & Crisis Management," below). If a patient is deemed to need psychiatric hospitalization based on the screening, they will be withdrawn from the study.

Assessments and Remuneration. In **Aim 2**, participants will complete a baseline assessment, an 8-week follow-up assessment and interview; in **Aim 3**, participants will complete a baseline assessment, an 8-week interview and an 8-week and 16-week computerized follow-up assessment. Follow-up assessments will take place online, on the telephone, or in private rooms at the PI's departmental office (separate from the ED) where privacy and confidentiality can be maintained (i.e., making sure no one can overhear the conversation).

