Participant confidentiality will be breached only to protect the safety and welfare of research participants and only in accordance with state and federal law. The exceptions to confidentiality include if the adolescent reports suicidality, homicidal thoughts, or that he/she is the victim of child abuse or neglect. If the adolescent reports suicidality or homicidality, parents will be notified, and an emergency psychiatric evaluation for inpatient hospitalization will be facilitated with the Pediatric Emergency Psychiatric Service at Rhode Island Hospital. If necessary, authorities will be notified. If child abuse or neglect is reported, a report will immediately be filed with the Department of Children, Youth and Families. This exception to breaking confidentiality – the case where a participant reveals child abuse, suicidality, or homicidality – will be explained in detail to both participants and parents prior to completing the assent/consent.

Finally, information collected in this research study will not be available to clinicians, parents, or to other researchers. All data will be collected specifically for use on this project.

Risk 3) Emotional Discomfort

Of note, members of the proposed mentorship team have substantial prior clinical and research experience with high-risk populations as evidenced through their biographical sketches. [name] has extensive clinical and research experience developing interventions for depressed, suicidal, and alcohol-abusing adolescents. [name] has extensive clinical and research experience with adolescent violence and substance abuse prevention.

Parental distress: If parents report feelings of distress as a result of being notified that their child is eligible for this research project, clinical resources will be offered. These include referrals for mental health counseling and information about violence hotlines and local community organizations.

Assessments: The assessment instruments are commonly used in research and clinical practice. We will minimize distress by presenting questions/program techniques in a supportive manner, assuring participants that they may refuse to answer questions that make them uncomfortable, and reminding them that they may terminate the assessment and/or intervention at any time.

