calming strategies. Staff will receive training in crisis assessment and management procedures in the event that participants reveal suicidal and/or homicidal ideation, child physical/sexual abuse, or concerns about safety. Drs. [name] (M.D., Emergency Medicine) and [name] (Ph.D., Clinical Psychology) will be responsible for providing regular supervision to research staff who have direct contact with patients including crisis procedures for suicide and homicide risk and clinical assessment and referral procedures for participants who are a danger to themselves or others. Supervision will focus on procedures for managing issues that could arise given the patient population, including potential crisis situations and/or adverse events.

Our crisis management procedures mirror those used by the Rhode Island Hospital Department of Psychiatry and Emergency Medicine clinical services. [name] has successfully used these safety protocols in studies at the proposed study site.

It is possible that situations will arise in which researchers are provided with information by children or families which they are legally and ethically obligated to disclose (e.g., suicidal or homicidal intent, harsh disciplinary practices, sexual abuse). All participants are informed in advance through the process of informed consent of the legal and ethical obligations of study staff should these issues arise. The consent and assent forms will clearly describe times when confidentiality must be broken, i.e., suicidality, homicidal thoughts, and a report of child physical or sexual abuse. Participant confidentiality will be breached only to protect the safety and welfare of research participants and only in accordance with state and federal law.

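### The exceptions to confidentiality that families are to be told about do not cover all the disclosures the plan makes, notably a severe depression score

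*Combined protocol and SAP*

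**What the plan says.** Section 14b.2, Risk 2 (Confidentiality), allows disclosure in general terms: "Participant confidentiality will be breached only to protect the safety and welfare of research participants". It then names the grounds: "The exceptions to confidentiality include if the adolescent reports suicidality, homicidal thoughts, or that he/she is the victim of child abuse or neglect". What will be explained to teens and parents before assent and consent is "the case where a participant reveals child abuse, suicidality, or homicidality". The section closes by saying that "information collected in this research study will not be available to clinicians, parents, or to other researchers". Risk 5 (Mandatory Reporting and Crisis Management) says the consent and assent forms will describe "times when confidentiality must be broken, i.e., suicidality, homicidal thoughts, and a report of child physical or sexual abuse".

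Other sections set out what staff will do with the information:

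- Section 14b.1, Referrals: "If an adolescent screens positive for severe depressive symptoms at any time during the study, regardless of eligibility for the study", then "the RA will discuss the score with the family, notify the attending pediatric emergency physician". The RA also offers to contact the pediatrician. Suicidality is handled in a separate paragraph.
- Approach, Eligibility and Enrollment: the attending is notified at PHQ-9 ≥ 20 or on a positive suicidal ideation item. Either is enough.
- Section 14b.2, Risk 3, Ongoing Safeguards: where a participant is found to need mental health treatment, the parents are told of the clinical need.
- Section 14b.2, Risk 3, Assessments: a severe score at baseline or follow-up triggers an evaluation, and telling the parent is tied to a finding of risk to self or others.
- Section 14b.1, Screening and Consent: "Adolescents and their parents will be informed that their responses to screening questionnaire indicate that they are eligible" for a program concerned with mental health and fighting.

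**The concern.** The participants are minors who answer questions about mood, fights and drug use while a parent is at the visit. If they and their parents are told of three exceptions and the plan routinely acts on more, the notice they receive is incomplete on a matter they would care about. The gap is widest for teens with a severe screening score. They are excluded from Aims 2 and 3, and written consent is taken only from eligible teens who agree to join, so these teens never see the written form. Whatever they are told in advance comes from the verbal script.

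There is also a practical problem for staff. An RA holding a severe score from a follow-up survey finds one instruction to discuss it with the family and another that makes telling the parent depend on an evaluation.

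**Working it through.** No formula or statistical input is involved, and the protocol gives no figure to reproduce. The check sets each disclosure against the three events to be explained: suicidality, homicidality and child abuse.

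1. **Severe score to family and attending (Referrals).** The trigger is the score. No suicidal ideation is needed and eligibility is irrelevant. It is outside the three events.
2. **PHQ-9 ≥ 20 to the attending (Eligibility and Enrollment).** The score and the ideation item are joined by *or*, so the score alone suffices. It is outside the three events and conflicts with the statement that clinicians will not have study information.
3. **Clinical needs to parents (Ongoing Safeguards).** The trigger is a need for mental health treatment, which is wider than the three events. It is outside the list.
4. **Severe score after enrolment.** Referrals applies throughout the study and has the score discussed with the family. Risk 3 has the teen evaluated first and ties notification to a finding of risk. For a teen with a severe score who is judged not to be at risk, the two give different answers.
5. **Eligibility to parents (Screening and Consent).** Eligibility requires both depressive symptoms and past-year peer violence. A parent who hears that the answers qualify the teen for such a program can infer a positive screen. No score or individual answer is given.
6. **Which teens count as severe.** The cut-off is ≥ 20 in Eligibility and Enrollment and > 20 in section 14a.1, and Screening and Consent treats scores between 5 and 20 as eligible. A teen scoring exactly 20 is therefore placed differently by different sections, including on whether that teen reaches the written form.

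The only arithmetic available concerns item 5, as eligible teens = enrolled ÷ consent rate. The protocol gives two trial sizes (120 in Aim 3 and Sample size; 50 per arm, so 100, in Study Randomization and section 14a.1). It gives three rates: 70% seen in Aim 1, a 65% acceptability target and a conservative 50%.

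- Lowest: 100 ÷ 0.70 = 143
- At the target: 120 ÷ 0.65 = 185
- Highest: 120 ÷ 0.50 = 240

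This counts families told of eligibility. It does not count severe-score disclosures, for which the protocol gives no rate.

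**The case against.** The best defence is that Risk 2 is wider than its list. It opens with a clause on safety and welfare, introduces the events with *include*, and places the blanket sentence after the exceptions, so that sentence can be read as subject to them. Severe depression fits such a clause. Section 14b.1 also has staff spell out when confidentiality may be broken, section 14b.2 has them explain procedures and risks in full, and Risk 5 has families told in advance of legal and ethical duties to disclose. This supplies a ground for disclosing a severe score. It does not repair the notice, because the only content given for it is the three events, and Risk 5 closes that list with *i.e.*

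A reader might infer three stronger things, none of which the documents support.

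- **That assent rests on a promise the plan breaks.** The blanket sentence is protocol text. Nothing shows that it is read to teens or printed in a form. The script is not reproduced, and the consent pages are not available to this review.
- **That parents are given every eligible teen's screening result.** They are told of eligibility. Parent and teen hear beforehand that answers may decide eligibility, Risk 3 anticipates parents' distress at that news, and a parent cannot consent to the program without knowing its purpose.
- **That 8- and 16-week outcomes will be under-reported.** Teens with severe scores at screening are not enrolled and supply no follow-up data. Only severe scores arising later could matter. The disclosure rules make no distinction between arms, and nothing in the protocol allows an effect to be estimated.

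**Conclusion.** The inconsistency is real and should be corrected. The disclosures in items 1 to 3 of the check are routine, fall outside the exceptions the plan says will be explained, and cannot stand beside an unqualified statement that clinicians and parents will not have study information. The Referrals and Risk 3 instructions also conflict for a severe score after enrolment. The eligibility notice is a lesser matter: it implies a positive screen and belongs in the advance notice, but it is not a disclosure of results.

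The point concerns what minors and parents are told and what staff do. It changes no sample size, error rate or estimate. About 143 to 240 families would be told of eligibility, assuming the stated enrolment is reached at one of the protocol's consent rates. The number of severe scores is unknown. The conclusion also assumes that the script and forms follow the protocol's description of them; if they already name the wider disclosures, only the protocol text needs correcting.

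**What to change.** Reconcile Eligibility and Enrollment, Referrals, and Risks 2, 3 and 5 of section 14b.2 so that they give one consistent account of who is told what, and when, about a severe score or a clinical need. This includes the score of exactly 20 and severe scores at baseline and follow-up. Which disclosure rule to keep is for the investigators and the IRB to decide and is not judged here.

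Then remove the blanket sentence in Risk 2, or make it expressly subject to the disclosures that remain. Have the verbal pre-screening script and the exception list in the consent and assent forms name each of them, including severe scores and the notice of eligibility to parents. The script matters most, since it is the only notice that reaches teens excluded for a severe score.

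The cost is a wording amendment through the IRB. Fuller warning carries a small risk of lowering some self-report; the Patient Screening paragraph already records that disclosure by teens is sensitive to how the screen is presented.
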